than there might be with a 5-point scale (13). The scale is rated as follows: 0: absence of pruritus; 1: mild pruritus (occasional slight itching/scratching); 2: moderate pruritus (constant or intermittent itching/scratching that does not disturb sleep) and 3: severe pruritus (bothersome itching/scratching that disturbs sleep).

Patients will be instructed on using the pruritus reporting system to complete the pruritus categorical scale at the screening visit. Patients will complete the categorical scale daily. Clinical sites will receive alerts when patients do not complete the pruritus reporting system items. Sites will be expected to contact patients who have missed 2 consecutive entries to encourage patient compliance. The Investigator will check patients' reports at each visit.

9.2.1.8 *Sick Leave/Missed School Days*

Patients who are employed or enrolled in school will be asked to report the number of sick leave/missed school days since the last study assessment. Patients will undergo this assessment at time points according to [Section 1.2](#).

The assessment tool is provided in the user guidance.

9.2.1.9 *Atopic Dermatitis Area Photographs*

At selected study sites, photographs will be taken of a representative area of AD involvement (eg, the lesional area used for EASI assessments on Day 1/baseline [pre-dose]). Subsequent photographs of the same area will be taken at Week 16 (end of treatment) and Week 28 (end of study).

Instructions for taking the photographs are provided in the photography reference manual.

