10.1.6 Unscheduled Visits

All attempts should be made to keep patients on the study schedule. Unscheduled visits may be necessary to repeat testing following abnormal laboratory results, for follow-up of AEs, or for any other reason, as warranted. During an unscheduled visit, any of the procedures noted may be performed, but not all are required.

The following information will be collected:

- Concomitant medications/procedures
- AEs

The following procedures and assessments will be conducted:

- Pruritus NRS and pruritus categorical scale
- POEM
- DLQI
- Assess sick leave/missed school days
- Vital signs
- IGA
- EASI
- BSA
- Photograph AD area (select sites only)
- Weight
- Laboratory testing:
 - Hematology and chemistry
 - Urinalysis
 - Urine pregnancy test (WOCBP only)
[REDACTED]
[REDACTED]
 - Functional dupilumab PK sample
 - Anti-dupilumab antibody sample

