4.4.2 Secondary Efficacy Variables

The secondary endpoints are:

- Proportion of patients with EASI-75 response (reduction of EASI score $\geq 75\%$ from baseline) at Week 16
- Proportion of patients with reduction of weekly average of peak daily pruritus NRS ≥ 4 from baseline to Week 16
- Proportion of patients with reduction of weekly average of peak daily pruritus NRS ≥ 3 from baseline to Week 16
- Percent change from baseline to Week 16 in weekly average of peak daily Pruritus NRS
- Change from baseline to Week 16 in weekly average of peak daily Pruritus NRS
- Percent change in EASI score from baseline to Week 16
- Change from baseline to Week 16 in percent BSA of AD involvement
- Change from baseline to Week 16 in DLQI
- Change from baseline to Week 16 in POEM
- Percent change from baseline to Week 2 in weekly average of peak daily Pruritus NRS
- Absolute and percent change from baseline to Week 16 in EQ-5D
- Proportion of patients who achieve reduction of IGA score by ≥ 2 from baseline to Week 16
- The proportion of patients with EASI-50 ($\geq 50\%$ improvement from baseline) at Week 16
- The proportion of patients with EASI-90 ($\geq 90\%$ improvement from baseline) at Week 16

- Proportion of patients achieving IGA 0 to 1 and a reduction of ≥ 2 points from baseline through Week 16
- Absolute and percent changes in EASI score from baseline through Week 16
- Absolute and percent changes in weekly average of peak daily pruritus NRS score from baseline through Week 16
- The proportion of patients who responded “absence of pruritus” or “mild pruritus” in the pruritus categorical scale at Week 16
- Number of days and proportion of patients with sick leave/missed school days

Eczema Area and Severity Index (EASI)

The EASI is a validated measure used in clinical practice and clinical trials to assess the severity and extent of AD ([Hanifin 2001](#)). Four AD disease characteristics (erythema, thickness [induration, papulation, edema], scratching [excoriation], and lichenification) will each be assessed for severity by the Investigator or designee on a scale of “0” (absent) through “3” (severe). In addition, the area of AD involvement will be assessed as a percentage by body area of head, trunk, upper limbs, and lower limbs, and converted to a score of 0 to 6. In each body region, the area is expressed as 0, 1 (1% to 9%), 2 (10% to 29%), 3 (30% to 49%), 4 (50% to 69%), 5 (70% to 89%), or 6 (90% to 100%).

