The EQVAS records the respondent’s self-rated health on a vertical, visual analogue scale where the endpoints are labeled “best imaginable health state (100)” and “worst imaginable health state (0)”. This information can be used as a quantitative measure of health outcome as judged by the individual respondents.

EQ-5D-3L will be assessed at the following visits: baseline (Day 1), Week 8, Week 16 (EOT), Week 28 (EOS), and early termination (ET) visit.

Pruritus Categorical Scale (PCS)

The PCS is a 4-point scale used to assess symptoms that has been used in clinical studies of AD and there is less of a tendency for patients to provide an “average” response than there might be with a 5-point scale ([Kaufmann 2006](#)). The scale is rated as follows: 0: absence of pruritus; 1: mild pruritus (occasional slight itching/scratching); 2: moderate pruritus (constant or intermittent itching/scratching that does not disturb sleep) and 3: severe pruritus (bothersome itching/scratching that disturbs sleep).

Patients will be instructed on using the pruritus reporting system to complete the PCS at the screening visit. Patients will complete the categorical scale daily. Clinical sites will receive alerts when patients do not complete the pruritus reporting system items. Sites will be expected to contact patients who have missed 2 consecutive entries to encourage patient compliance. The Investigator will check patients’ reports at each visit.

For each day, if there are multiple PCS scores collected on the same day, the maximum (worst) of all the scores collected will be chosen. For each week, calculate round prorated average of

collected scores for Category Score. For example, if there are 3 scores in a week, the prorated average = (score1 + score2 + score3)/3 round to 1.0.

The baseline PCS is defined as the round prorated average of the PCSs reported continuously for 7 days right before and on the baseline visit (i.e. study day -6 to day 1).

Sick Leave/Missed School Days

Patients who are employed or enrolled in school will be asked to report the number of sick leave/missed school days since the last study assessment. Patients will undergo this assessment at the following visits: baseline (Day 1), Week 4, Week 8, Week 12, Week 16 (EOT), Week 20, Week 24, Week 28 (EOS), ET and unscheduled visits.

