6.4 Analysis Visit Window

Data analyzed by-visit-analysis (including efficacy, laboratory data, visit sign, ECG, ADA) will be summarized by the study scheduled visits described [Appendix 10.2](#), "Schedule of Event". The analysis visit windows will be exhaustive so that all available values obtained from unscheduled visits, early termination visit (ETV) and end of treatment (EOT)/end of study (EOS) have the potential to be summarized. No analysis visit windows will be applied for the study scheduled visits.

The following analysis visit windows will be used to map the unscheduled visits, ETV and EOT/EOS visits, based on the study day:

Time window for efficacy variables

Visit No.	Visit	Targeted Study Days*	Analysis Window in Study Days		
			IGA, EASI, BSA, POEM, DLQI	EQ-5D	Sick-Leave/Missed School Days
1	Screening	<1	<1		
2	Baseline	1	1	≤1	≤1
3	Week 2	15	[2,22]		
4	Week 4	29	[23, 43]		[2, 43]
5	Week 8	57	[44, 71]	[2, 85]	[44, 71]
6	Week 12	85	[72, 99]		[72, 99]
7	Week 16 (End of Treatment)	113	[100, 127]	[86, 155]	[100, 127]
8	Week 20	141	[128, 155]		[128, 155]
9	Week 24	169	[156, 183]		[156, 183]
10	Week 28 (End of Study)	197	≥184	≥156	≥184

*Study days are calculated from 1st day of dupilumab injection (1st day of randomization if the patient is not treated)

Time window for safety variables

Visit No.	Visit	Targeted Study Days*	Analysis Window in Study Days					
			Vital Signs	Weight	ECG	Hematology and Chemistry	Urinalysis	Serum Pregnancy Test
1	Screening	<1	<1	<1	<1	<1	<1	<1
2	Baseline	1	1	1		1	1	≤1
3	Week 2	15	[2,22]					
4	Week 4	29	[23, 43]					[2, 43]
5	Week 8	57	[44, 71]			[2, 85]		[44, 71]
6	Week 12	85	[72, 99]					≥72

7	Week 16 (End of Treatment)	113	[100, 127]	[86, 155]	[86, 155]	[86, 155]	[2, 155]	[2, 155]	
8	Week 20	141	[128, 155]						
9	Week 24	169	[156, 183]						
10	Week 28 (End of Study)	197	≥ 184	≥ 156					

*Study days are calculated from 1st day of dupilumab injection (1st day of randomization if the patient is not treated)

Time window for other variables

Visit No.	Visit	Targeted Study Days*	Analysis Window in Study Days	
				PK/Drug Concentration, ADA
1	Screening	<1	<1	
2	Baseline	1	1	≤ 1
3	Week 2	15		
4	Week 4	29		
5	Week 8	57		
6	Week 12	85		[2, 99]
7	Week 16 (End of Treatment)	113	[2, 155]	[2, 155]
8	Week 20	141		
9	Week 24	169		
10	Week 28 (End of Study)	197	≥ 156	≥ 156

*Study days are calculated from 1st day of dupilumab injection (1st day of randomization if the patient is not treated)

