In general, the following order will be used to select the record for analysis at given visit:

1. Scheduled visit
2. Early termination (ET) or end of study (EOS), whichever comes first if scheduled visit not available
3. Unscheduled visit if both scheduled visit and ETV/EOT/EOS are not available

For the multiple measurements of the same test in the same window, the following rules will be used to pick up the analysis value:

- If multiple valid values of a variable within an analysis visit window, the closest from the target study day will be selected.
- If the difference is a tie, the value after the targeted study day will be used.
- If multiple available values of a variable exist within a same day, then the first value of the day will be selected.

Both scheduled and unscheduled measurements will be considered for determining abnormal/PCSA values from laboratory, vital sign or ECG as well as the baseline values.

For the ePRO data collected daily, the analysis visit windows will be implemented following the procedures below:

Step 1: Derive the study day,

- If diary date \geq 1st injection date, then diary study day=diary date – 1st injection date +1;
- Otherwise diary study day=diary date – 1st injection date

Randomization date will be used instead of 1st injection date for patients randomized but not treated.

Step 2: Windows are defined as -6 to 1 = BL, 2 to 8 = week 1, 9 to 15 = week 2, etc, with 7 days interval between visit windows.

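### Sick-leave/missed-school days are counted since the previous assessment, but SAP 6.4 keeps one record per visit, so days reported at an unscheduled visit can drop out

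*SAP*

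**What the plan says.** The last secondary efficacy endpoint listed in SAP 4.4.2 is "Number of days and proportion of patients with sick leave/missed school days". It names no visit, time span or rule for combining reports.

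Protocol 9.2.1.8 describes the item: "Patients who are employed or enrolled in school will be asked to report the number of sick leave/missed school days since the last study assessment". SAP 4.4.2 repeats this and lists collection at baseline, Weeks 4, 8, 12 and 16, and then "Week 20, Week 24, Week 28 (EOS), ET and unscheduled visits". At an unscheduled visit the item is optional. Protocol 10.1.6 says that "any of the procedures noted may be performed, but not all are required".

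SAP 6.4 opens its windowing rule with "Data analyzed by-visit-analysis (including efficacy, laboratory data, visit sign, ECG, ADA) will be summarized by the study scheduled visits". Its efficacy table has a separate column for sick leave/missed school days: [2, 43] for Week 4, [44, 71] for Week 8, [72, 99] for Week 12 and [100, 127] for Week 16. One record is then selected per visit. A scheduled record comes first and an early-termination or end-of-study record second. The third choice is "Unscheduled visit if both scheduled visit and ETV/EOT/EOS are not available". Several values in one window are resolved by closeness to the target day. Unscheduled values are otherwise brought in only for abnormal/PCSA findings and for baseline.

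**The concern.** Selecting one record suits a status score such as IGA or EASI, where the scheduled value describes the patient on that day and a discarded earlier value leaves no gap. Sick leave is an interval count. Once a report has been taken, the next one starts from there, so a discarded report removes days that no other record holds.

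Both parts of the endpoint are exposed. The number of days is understated for an affected patient. A patient whose only absences were reported at an unscheduled visit would be counted as having had none. This can happen to an employed patient with complete data and no rescue, so the rules for missing data and rescue do not deal with it.

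**Working it through.** The documents give no figure for this endpoint, so there is none to reproduce. The 94% power in SAP 2.2 belongs to the primary endpoint and is unaffected.

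**Inputs.** Scheduled sick-leave reports fall on Days 1, 29, 57, 85 and 113 (SAP Appendix 10.2). The windows are those in SAP 6.4. Assume that the item is completed at one unscheduled visit on Day u, that the patient attends all scheduled visits, and that recall runs from the last completed sick-leave report.

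**Step 1: where the unscheduled report lands.**

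| Interval | Possible u | Maps to preceding scheduled window | Maps to following scheduled window |
|---|---|---|---|
| Day 1 to 29 | 2–28 | none | 27 days (Week 4) |
| Day 29 to 57 | 30–56 | 14 days, 30–43 (Week 4) | 13 days, 44–56 (Week 8) |
| Day 57 to 85 | 58–84 | 14 days, 58–71 (Week 8) | 13 days, 72–84 (Week 12) |
| Day 85 to 113 | 86–112 | 14 days, 86–99 (Week 12) | 13 days, 100–112 (Week 16) |

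In every cell the window already holds a scheduled record, so the unscheduled report is not used. The loss does not depend on which window it maps to.

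**Step 2: how much is lost.** With s the preceding scheduled day, the share of the interval lost is (u − s)/28.

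- Week 4 to Week 8, s = 29: Day 36 gives 7/28 = 25%, Day 43 gives 14/28 = 50%, and Day 50 gives 21/28 = 75%. Days 36 and 43 map to the Week 4 window, although their reports cover time after Week 4.
- Week 8 to Week 12, s = 57, u from 58 to 84: the loss runs from 1 to 27 days. If u is uniform (assumption), the mean is (1 + 27)/2 = 14 days, and 14/28 = 50%.
- The other three intervals have the same 27 possible positions and the same mean. Over Day 1 to Day 113 (112 days), one such visit costs on average 14/112 = 12.5% of coverage.

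**Step 3: one patient.** Suppose 5 sick days on Days 60–64, reported at an unscheduled visit on Day 66, and 1 sick day on Day 80, reported at Week 12 (Day 85). Day 66 maps to [44, 71], where the scheduled Week 8 record has priority. The analysed count after Week 8 is 1 of 6 days. Without the Day 80 absence it would be 0, and the patient would appear to have had no sick leave in that interval.

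**Step 4: is there a summing rule elsewhere?** SAP 4.4.2, 5.7 and Appendix 10.1 contain none for this item.

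**The case against.** Much of the other side is sound, and it limits the point.

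- A reader might infer that every unscheduled visit resets the count. It does not: procedures there are optional, and a visit for a repeat laboratory test may not include the item.
- The recall anchor is unclear. The form is in the user guidance, which is not among the documents. The Week 2 visit has no sick-leave item, so even at Week 4 the last study assessment could mean Week 2 or baseline. If the form anchors recall to the last scheduled visit, nothing is lost and summing would double count.
- SAP 6.4 introduces its selection order as a general rule, and the endpoint names no visit. A programmer could total all records. But nothing says so, and the item has its own window column, so the written rule leads to discarding.
- A reader might infer bias toward zero because unscheduled visits follow worsening and would be commoner on placebo. The documents give no rate, overall or by arm. The reasons named in Protocol 10.1.6 are abnormal laboratory results, follow-up of adverse events and any other reason, which could favour either arm. For visits made just before rescue, SAP 5.7 already sets later data to missing or counts non-response, so the later report is not simply analysed as a low count.
- Larger losses can be constructed. A patient missing 1 day a week, with completed unscheduled reports on Days 50, 78 and 106, keeps 4 + 1 + 1 + 1 = 7 of 16 days. That needs three such visits, each 7 days before a scheduled one, and says nothing about a typical patient.

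**Conclusion.** The defect stands in conditional form. When the item is completed at an unscheduled visit, the patient also attends the scheduled visits, and recall runs from the last sick-leave report, SAP 6.4 as written understates that patient's days and may turn a patient with sick leave into one without. The unscheduled report survives only where the window has no scheduled or early-termination/end-of-study record. An early-termination report sharing a window with a scheduled record is lost in the same way.

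The 50% (one interval) and 12.5% (treatment period) averages are per affected patient, for one such visit with uniform timing. They are not trial-level estimates. A claim that the treatment difference is biased in a given direction is not supported.

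Severity is low. The endpoint applies only to employed or enrolled patients and is absent from the testing hierarchy in SAP 5.7.2. The primary analysis is untouched.

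**What to change.** In SAP 4.4.2 and 6.4:

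1. Exempt sick leave/missed school days from one-record-per-visit selection.
2. Define the last study assessment as the last completed sick-leave assessment, after checking the wording of the form.
3. For each interval, sum all scheduled, unscheduled and early-termination reports dated after one scheduled sick-leave visit, up to and including the next. Do not group by the existing windows, which would place a Day 36 report with Week 4.
4. For the treatment-period total, sum all reports dated after Day 1 up to and including Week 16, and present the number of days covered with it.
5. Define any sick leave as a summed count above 0.
6. If the form anchors recall to the last scheduled visit, state that and do not sum.

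The cost is a few lines of SAP text and some programming before database lock. The data are already collected.

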7 INTERIM ANALYSIS

No interim analysis is planned.

Sponsor may run a first step analysis when all patients complete their 16-week treatment period.

8 SOFTWARE

All analyses will be done using SAS Version 9.4 or above.

10 APPENDIX

10.1 Summary of Statistical Analyses

Efficacy Analysis:

Endpoint	Analysis Population	Primary Statistical Method	Supportive/Sensitive Statistical Method	Subgroup Analysis	Other Analyses
Proportion of patients with both IGA 0 to 1 (on a 5-point scale) and a reduction from baseline of ≥ 2 points at Week 16	ITT population	Cochran-Mantel-Haenszel test / define missing as treatment failure	Cochran-Mantel-Haenszel test on observed value or LOCF, and on PP population	Yes	Line plot, forest plot
Secondary continuous variables	ITT population	MI	MMRM, ANCOVA with LOCF	Yes for EASI and NRS endpoints	Line plot
Secondary categorical variables	ITT population	Cochran-Mantel-Haenszel test / define missing as treatment failure	Cochran-Mantel-Haenszel test / LOCF	Yes for EASI and NRS endpoints	Line plot, forest plot

Safety Analyses:

Endpoint	Analysis Populations	Statistical Method	Supportive Analysis	Subgroup Analysis	Other Analyses
Adverse Events	Safety population	Descriptive statistics	No	No	No
Laboratory Measures	Safety population	Descriptive Statistics	No	No	No
Vital sign	Safety population	Descriptive Statistics	No	No	No
Physical Examination	Safety population	Descriptive Statistics	No	No	No
ECG	Safety population	Descriptive Statistics	No	No	No

10.2 Schedule of Events

Study Procedure	SCR	RND	Treatment								EOT	Follow-up		EOS	Unscheduled visit ^a (if applicable)	Early termination (if applicable)
	V1	V2	V3	V4		V5		V6		V7	V8	V9	V10			
	W0	W2	W4	W6	W8	W10	W12	W14	W16	W20	W24	W28				
	D-7 to D-35	D1	D15	D29	D43	D57	D71	D85	D99	D113	D141	D169	D197			
			±3d	±3d	±3d	±3d	±3d	±3d	±3d	±3d	±3d	±3d	±3d			
Screening/baseline																
Informed consent	X															
Inclusion/exclusion criteria	X	X														
Medical history/ demographics	X															
Randomization		X														
Training on pruritus reporting system ^b	X															
Treatment																
Injection training/observation		X	X	X		X		X								
Administer IMP ^c		X	X	X	X	X	X	X	X							
Dispense/review patient dosing diary ^d				X		X		X		X						
IMP dispensation/account ^e					X		X		X		X					
Con meds/procedures	X	X	X	X		X		X		X	X	X	X	X	X	
Efficacy^{f,g}																
Pruritus NRS (daily) ^b	X	X	X	X		X		X		X	X	X	X	X	X	
Pruritus categorical scale (daily) ^b	X	X	X	X		X		X		X	X	X	X	X	X	
POEM, DLQI ^h	X	X	X	X		X		X		X	X	X	X	X	X	
EQ-5D ^h		X			X				X			X			X	
IGA, EASI, BSA	X	X	X	X		X		X		X	X	X	X	X	X	
Assess sick-leave/missed school days		X		X		X		X		X	X	X	X	X	X	
Photograph AD area (selected sites) ⁱ		X								X		X	X	X	X	

Study Procedure	SCR	RND	Treatment							EOT	Follow-up		EOS	Unscheduled visit ^a (if applicable)	Early termination (if applicable)	
	VISIT(V)	V1	V2	V3	V4		V5		V6		V7	V8	V9	V10		
	Week(W)		W0	W2	W4	W6	W8	W10	W12	W14	W16	W20	W24	W28		
	Day (D)	D-7 to D-35	D1	D15	D29	D43	D57	D71	D85	D99	D113	D141	D169	D197		
	Visit Window (d)			±3d	±3d	±3d	±3d	±3d	±3d	±3d	±3d	±3d	±3d	±3d		
Safety^f																
Weight		X	X									X			X	X
Height		X														
Vital signs		X	X	X	X		X		X		X	X	X		X	X
Physical examination ^j		X									X		X			X
Electrocardiogram		X									X		X			X
Adverse events		X	X	X	X		X		X		X	X	X		X	X
Laboratory Testing^f																
HIV ab, HBsAg, HbsAb, HBcAb ^k , and Hep C Ab ^k		X														
Hematology and chemistry		X	X				X				X		X		X	X
Urinalysis		X	X								X		X		X	X
Pregnancy test (WOCBP only)	Serum	Urine		Urine		Urine		Urine		Serum		Serum		Urine		Serum
██████████	████	████								████				████	████	
██████████	████	████								████				████	████	
██████████ ████████		████												████	████	
ANA, anti-dsDNA (if ANA positive)	X															
PK/Drug Concentration and ADA Samples^f																
Functional dupilumab PK sample			X						X		X		X		X	X
Anti-dupilumab antibody sample			X						X		X		X		X	X

Abbreviations: AD = atopic dermatitis, ADA = anti-drug antibody, ANA = anti-nuclear antibody, anti-dsDNA = anti-double-strand DNA, BSA = body surface area, DLQI = Dermatology Life Quality Index.

Abbreviations: AD = atopic dermatitis, ADR = antidiag antibody, ATX = anti-thymocyte, anti-CD34+, anti-double strand DNA, BSA = body surface area, EQ = Dermatology Euro Quality Index, EASI = Eczema Area and Severity Index, EQ-5D = EuroQol five dimensions questionnaire, EOS = end-of-study, EOT = end-of-treatment, HbCAb = hepatitis B core antibody, HBsAb = hepatitis

B surface antibody, HBsAg = hepatitis B surface antigen, Hep C Ab = hepatitis C antibody, HIV ab = human immunodeficiency virus antibody, IGA = investigator global assessment.

[REDACTED], IMP = investigational medicinal product.

NRS = numerical rating scale, PK = pharmacokinetics, POEM = Patient Oriented Eczema Measure, RND = randomization, SCR = screening.

WOCBP = woman of child bearing potential

- a During an unscheduled visit, any of the study procedures noted may be performed, but not all are required.
- b Patients will be trained at the screening visit on using the appropriate diary system to report pruritus daily and provide other information as required. Investigators will check patients' reports at each visit.
- c Patients will be monitored at the study site for a minimum of 30 minutes after the IMP administration for any signs or symptoms of a hypersensitivity reaction. Adverse event assessments will be done at 30 minutes (± 10 minutes) post-injection.
- d For patients who choose to self-administer the IMP at Weeks 6, 10, and 14, counsel patient on proper dosing diary completion/reporting of each dose of study drug that is administered outside of the clinic.

- e For patients who choose to self-administer the IMP, the IMP will be dispensed to the patient for the dose that will be administered before the next clinic visit. Patients will return the original kit box for the prefilled syringe at each clinic visit.
- f To be collected before the injection of the IMP.
- g Assessments/procedures should be conducted in the following order: patient reported outcomes (PROs), Investigator assessments, safety and laboratory assessments, and then administration of the IMP.
- h All questionnaires will be administered before any invasive procedures (blood draws, IMP injection, etc).
- i Selected sites only - photograph AD area
- j If patients have any symptom or sign of ocular surface diseases, eg, conjunctivitis and blepharitis, at screening or during study period, ophthalmological examinations should be done.
- k Hepatitis B virus (HBV) DNA testing should be performed during screening period for patients presenting with HBsAg (-) and HBcAb (+). In case of results showing HCV Ab positive, an HCV RNA testing may be performed to rule out a false positivity, if the Investigator believes the patient is a false positive.

[REDACTED]

10.3 Criteria for Treatment-Emergent Potentially Clinical Significant Abnormality (PCSA) for Dupilumab AD studies

Parameter	Treatment Emergent PCSA	Comments
Clinical Chemistry		
ALT*	
>3 and \leq 5 ULN and baseline \leq 3 ULN*
 
>5 and \leq 10 ULN and baseline \leq 5 ULN
 
>10 and \leq 20 ULN and baseline \leq 10 ULN
 
>20 ULN and baseline \leq 20 ULN
	
Enzyme activity must be expressed in ULN, not in IU/L.
 
Concept paper on DILI – FDA draft Guidance Oct 2007.
 
Each category is calculated independently.
 
* At least one level is required, multiple levels are optional for phase 2/3 studies. If it is desirable to get the distribution across the different PCSA levels, additional shift table on \leq3, >3 to \leq5, >5 to \leq10, >10 to \leq20, and > 20 category for baseline vs. post baseline may be provided

AST*	
>3 and \leq 5 ULN and baseline \leq 3 ULN*
 
>5 and \leq 10 ULN and baseline \leq 5 ULN
 
>10 and \leq 20 ULN and baseline \leq 10 ULN
 
>20 ULN and baseline \leq 20 ULN
	
Enzyme activity must be expressed in ULN, not in IU/L.
 
Concept paper on DILI – FDA draft Guidance Oct 2007.
 
Each category is calculated independently.
 
* At least one level is required, multiple levels are optional for phase 2/3 studies. If it is desirable to get the distribution across the different PCSA levels, additional shift table on \leq3, >3 to \leq5, >5 to \leq10, >10 to \leq20, and > 20 category for baseline vs. post baseline may be provided

Alkaline Phosphatase	>1.5 ULN and baseline \leq 1.5 ULN	
Enzyme activity must be expressed in ULN, not in IU/L.
 
Concept paper on DILI – FDA draft Guidance Oct 2007.

Total Bilirubin*	
>1.5 and \leq 2 ULN and baseline \leq 1.5 ULN*
 
>2 ULN and baseline \leq 2.0 ULN
	
Must be expressed in ULN, not in μmol/L or mg/L. Categories are cumulative.
 
Concept paper on DILI – FDA draft Guidance Oct 2007.
 
* At least one level is required, multiple levels are optional for phase 2/3 studies. If it is desirable to get the distribution of significant level, additional shift table on \leq1.5, >1.5 to \leq2.0 and > 2.0 category for baseline vs. post baseline may be provided

Parameter	Treatment Emergent PCSA	Comments
Conjugated Bilirubin	(Direct Bilirubin >35% Total Bilirubin and Total Bilirubin >1.5 ULN) and (Direct Bilirubin <=35% Total Bilirubin or Total Bilirubin <=1.5 ULN) at baseline	Conjugated bilirubin dosed on a case-by-case basis.
ALT and Total Bilirubin	(ALT>3 ULN and TBILI>2 ULN) and baseline (ALT <=3 ULN or TBILI <=2 ULN)	Concept paper on DILI – FDA draft Guidance Oct 2007.
CPK*	>3 and \leq 10 ULN and baseline \leq 3ULN* >10 ULN and baseline \leq 10ULN	FDA Feb 2005. Am J Cardiol April 2006. Categories are cumulative. * At least one level is required, multiple levels are optional for phase 2/3 studies. If it is desirable to get the distribution of significant level, additional shift table on \leq 3, >3 to \leq 10, and $>$ 10 category for baseline vs. post baseline may be provided
Creatinine	\geq 150 μ mol/L (Adults) and baseline < 150 μ mol/L \geq =30% change from baseline and <100% change from baseline \geq 100% change from baseline	Benichou C., 1994. 3 independent criteria
Uric Acid		Harrison- Principles of internal Medicine 17 th Ed., 2008.
Hyperuricemia	>408 μ mol/L and <=408 μ mol/L at baseline	
Hypouricemia	<120 μ mol/L and \geq 120 μ mol/L at baseline	Two independent criteria
Blood Urea Nitrogen	\geq 17 mmol/L and <17 mmol/L at baseline	Two independent criteria
Chloride		Two independent criteria
Hypochloremia	<80 mmol/L and baseline \geq 80 mmol/L	
Hyperchloremia	>115 mmol/L and baseline \leq 115 mmol/L	
Sodium		Two independent criteria
Hyponatremia	\leq 129 mmol/L and baseline > 129 mmol/L	
Hypernatremia	\geq 160 mmol/L and baseline <160 mmol/L	
Potassium		FDA Feb 2005.
Hypokalemia	<3 mmol/L and baseline \geq 3 mmol/L	Two independent criteria
Hyperkalemia	\geq 5.5 mmol/L and baseline <5.5 mmol/L	
Total Cholesterol	\geq 7.74 mmol/L and < 7.74 mmol/L at baseline	Threshold for therapeutic intervention.
Triglycerides	\geq 4.6 mmol/L and < 4.6 mmol/L at baseline	Threshold for therapeutic intervention.

Parameter	Treatment Emergent PCSA	Comments
Glucose		
Hypoglycaemia	(≤3.9 mmol/L and <LLN) and (>3.9 mmol/L or ≥LLN) at baseline	ADA May 2005.
Hyperglycaemia	≥11.1 mmol/L (unfasted); ≥7 mmol/L (fasted) and < 11.1 mmol/L (unfasted); <7 mmol/L (fasted) at baseline	ADA Jan 2008.
HbA1c	>8% and ≤ 8% at baseline	
Albumin	≤25 g/L and >25 g/L at baseline	
CRP	>2 ULN or >10 mg/L (if ULN not provided) and ≤2 ULN or ≤10 mg/L (if ULN not provided) at baseline	FDA Sept 2005.
Hematology		
WBC	<3.0 Giga/L and ≥3.0 Giga/L at baseline (Non-Black); <2.0 Giga/L and ≥2.0 Giga/L at baseline (Black) ≥16.0 Giga/L and < 16 Giga/L at baseline	To be interpreted only if no differential count available.
Lymphocytes	>4.0 Giga/L and ≤ 4.0 Giga/L at baseline	
Neutrophils	<1.5 Giga/L and ≥1.5 Giga/L at baseline (Non-Black); <1.0 Giga/L and ≥1.0 Giga/L at baseline (Black)	International Consensus meeting on drug-induced blood cytopenias, 1991. FDA criteria.
Monocytes	>0.7 Giga/L ≤ 0.7 Giga/L at baseline	
Basophils	>0.1 Giga/L ≤ 0.1 Giga/L at baseline	
Eosinophils	(>0.5 Giga/L and >ULN) and (<=0.5 Giga/L or ≤ ULN at baseline)	Harrison- Principles of internal Medicine 17 th Ed., 2008.
Hemoglobin	≤115 g/L and > 115 g/L at baseline for male; ≤95 g/L and > 95 g/L at baseline for Female. ≥185 g/L and <185 g/L at baseline for Male; ≥165 g/L and < 165 g/L at baseline for Female Decrease from Baseline ≥20 g/L	Three criteria are independent. Criteria based upon decrease from baseline are more relevant than based on absolute value. Other categories for decrease from baseline can be used (≥30 g/L, ≥40 g/L, ≥50 g/L).
Hematocrit	≤0.37 v/v and > 0.37 v/v at baseline for Male; ≤0.32 v/v and > 0.32 v/v at baseline for Female ≥0.55 v/v and < 0.55 v/v at baseline for Male; ≥0.5 v/v and < 0.5 v/v at baseline for Female	Two Criteria are independent

Parameter	Treatment Emergent PCSA	Comments
RBC	Female <3 Tera/L and baseline \geq 3 Tera/L \geq 6 Tera/L and baseline < 6 Tera/L Male <4 Tera/L and baseline \geq 4 Tera/L \geq 7 Tera/L and baseline < 7 Tera/L	Unless specifically required for particular drug development, the analysis is redundant with that of Hb. Otherwise, consider FDA criteria.
Platelets	<100 Giga/L and \geq 100 Giga/L at baseline \geq 700 Giga/L and < 700 Giga/L at baseline	International Consensus meeting on drug-induced blood cytopenias, 1991. Two independent criteria
Urinalysis		
pH	\leq 4.6 and $>$ 4.6 at baseline \geq 8 and < 8 at baseline	Two independent criteria
Vital signs		
HR	\leq 50 bpm and decrease from baseline \geq 20 bpm \geq 120 bpm and increase from baseline \geq 20 bpm	To be applied for all positions (including missing) except STANDING.
SBP	\leq 95 mmHg and decrease from baseline \geq 20mmHg \geq 160 mmHg and increase from baseline \geq 20 mmHg	To be applied for all positions (including missing) except STANDING.
DBP	\leq 45 mmHg and decrease from baseline \geq 10 mmHg \geq 110 mmHg and increase from baseline \geq 10 mmHg	To be applied for all positions (including missing) except STANDING.
Weight	\geq 5% increase from baseline \geq 5% decrease from baseline	FDA Feb 2007.

